4.4 Sample size calculation

TB31F is a first in human observational safety trial in healthy volunteers, designed to identify safety concerns associated with TB31F administration at different dosages. A total of twenty-five healthy adults (males and females) aged 18 – 35 will be divided over five groups. Each group will include five subjects. The study's original sample size of n=20 (four intravenous groups of n=5), was calculated to have a 90% chance of observing at least 1 event if the true rate of such an event is 10.87% or more; and there is a 90% chance of observing no events if the true rate is 0.52% or less. The 5th (subcutaneous) was subsequently pragmatically chosen to have the same size. Sample size for each group is appropriate for mAb administration Phase 1 trials based on similar trial designs for HIV, CMV, and anthrax monoclonal antibody prophylactic studies [13-15]. This is a small Phase 1 study; therefore, it is largely descriptive and is intended to provide primarily safety data of 4 escalating intravenous doses of mAb TB31F and one subcutaneous dose of mAb TB31F. Comparative statistics will be performed but will have low power to detect anything other than very large differences between the groups. 5 reserve subjects will be recruited (1 reserve subject per group).

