
Local reactogenicity to SC administration of TB31F
	
MAb TB31F has never previously been administered subcutaneously in humans. Subcutaneous administration of TB31F may cause the subject to experience temporary pain and/or burning sensation at the site of administration.
	
All study subjects will receive premedication with paracetamol and clemastine. Experienced and qualified medical personnel will place the subcutaneous administration and counsel the subject. Every injection will be carefully monitored to evaluate the occurrence of local adverse events.
 
Subjects will be observed closely for at least 60 minutes following administration of the mAb TB31F product with appropriate medical treatment readily available in case of (severe) adverse events. In case of tolerability concerns, mAb TB31F may be diluted in normal saline for injections prior to subcutaneous administration, as described in the Pharmacy Manual.

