8.3.3 Inclusion visit (visit 2)

Subjects meeting the eligibility criteria during screening (section 4.2 and 4.3) will be invited back for enrolment into the study at the inclusion visit, which will occur prior to the planned administration day. Baseline assessments will be taken on the inclusion day. For each subject, study start (day 0) will be defined as the day of mAb administration. For subjects that do not show up for inclusion visit (visit 2), alternate subjects may be used. At study inclusion, the following activities will occur:

- Patient history will be taken and all adverse events that have occurred since screening will be noted. Only subjects who still meet the inclusion criteria will be included to receive mAb TB31F;
- Blood specimens will be collected for routine clinical laboratory testing of biochemical and hematological parameters;
- A urine specimen will be collected for toxicology screening and for females a pregnancy test

if the subject is of childbearing potential;

- Subject will be issued symptom diaries and a thermometer to record any local and systemic symptoms and medication use;
- All subjects will be issued an emergency notification card that details their participation in the study and provides contact phone numbers of the investigators.
- Since TB31F is administered at the Medium Care, subject may undergo presumptive testing for SARS-CoV2 (e.g. nasopharynx/throat swab for PCR) at inclusion in accordance with current Radboudumc MC guidelines.

8.3.4 mAb TB31F inoculation visit (visit 3)

The purpose of this visit is to inoculate enrolled subjects with mAb TB31F. On the day of mAb administration, the subjects will be admitted to the Medium Care Unit for approximately 8-10 hours. Subjects will be briefly assessed regarding any new medical events since the inclusion visit. Temperature, blood pressure, and pulse rate will be recorded. A repeat measurement of body weight may be performed. To confirm eligibility, results of all assessments will be reviewed. If the subject is still eligible for participation, the following activities will occur as detailed in section 8.3.18:

- The subject will have one or two intravenous dwelling catheters inserted into the antecubital vein of the arm.
- The subject will receive premedication: 1000mg paracetamol orally and 2mg clemastine intravenously.
- mAb TB31F product will be prepared by pharmacy staff based on group assignment and study subject weight in groups 1 up till group 4.

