- mAb TB31F will be administered by slow intravenous drip (see Appendix 2 for infusion rates) in group 1 up till group 4. The infusion rate will be reduced by 50% for mild reactions; and terminated for severe infusion reactions. MAb TB31F will be administered subcutaneously by slow injection in group 5, divided equally between two injection sites (1mL per site). Subjects will be observed directly for at least 60 minutes after the infusion. One intravenous dwelling catheter may be removed following drug product administration.
- Collection of serum/plasma for pharmacokinetic and pharmacodynamic measurements will be done at the following time points: 0 hours, EOI and 1, 3, and 6 hours after product administration. Subjects may leave the Medium Care Unit after 6 hours and return the next day to the clinical research center for the 24-hour blood sampling time point.
- Vital signs, adverse events (solicited and unsolicited) and blood will be collected at each time point as indicated in section 8.3.18.
- A list of solicited local and systemic symptoms will be reviewed with the subject at 0, EOI, 1, 3 and 6 hours (day 1) and 24 hours (day 2). If the occurrence of an adverse event or use of medication is confirmed by the study physician, it is recorded in the clinical trial database.

- After leaving the hospital, subjects will be asked to examine the site of infusion and record local signs and symptoms for seven days including bruising, erythema, swelling or induration. Subjects will be asked to measure their oral temperature daily until day 7. Subjects will be asked to record any AEs in the memory aid booklet until day 84. At the end of the study, the memory aid will be collected and kept as source data with the subject's study file.

All inoculations are performed by a trained nurse under the supervision of one of the clinical investigators. Another clinical investigator will be on call in case of emergency. Local hospital procedures will be followed. Study subjects will be monitored at the Medium Care Unit on the day of TB31F administration. The venous catheter will be removed at the end of visit 3 (day of product administration) and subjects will be discharged from the Medium Care Unit. Follow-up visits will take place as described in section 8.3.18.

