9.4.1 Adverse event data collection

Signs and symptoms will be recorded in study diaries and reviewed during admission at the clinical trial research center, at all follow-up visits, and whenever a trial volunteer reports signs or symptoms to the trial physician between visits.

Solicited adverse events

After administration with mAb TB31F the following systemic signs and symptoms will be solicited until 28 days after infusion:

Fever, headache, myalgia, fatigue, chills, and rash. The time points that these symptoms are solicited is indicated in section 8.3.18.

After the administration of mAb TB31F the following local signs and symptoms will be solicited until 7 days after administration:

Pain at injection site and redness/swelling at injection site. The time points that these symptoms are solicited is indicated in section 8.3.18.

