10.1 Primary study parameter(s)

The number of subjects enrolled, completed, or withdrawn will be summarized. Reasons for withdrawal, when known, will be provided. Demographic data will be summarized by descriptive statistics and will include total number of observations (n), mean, standard deviation (SD) and range for continuous variables, and number and percentages for dichotomous variables. The primary safety, and reactogenicity outcomes will include all subjects who meet the eligibility criteria, receive study product mAb TB31F, and for whom safety data are available.

Safety Analyses

For the safety analysis, data from all subjects who received a dose of mAb TB31F and for whom safety data are available will be included. All analyses will be descriptive. Data will be presented by dose, overall/dose and overall/subject. Results will be summarized by study group. The percentage of subjects with at least one local AE (solicited and unsolicited), with at least one general AE (solicited and unsolicited) and with any AE during the solicited follow-up period will be tabulated with exact 95% CI (two-sided). No multiplicity adjustment will be implemented in analysis. The same calculations will be performed for AEs rated as grade 3. The percentage of subjects reporting each individual solicited local and general AE during the solicited follow-up period will be tabulated with exact 95% CI. The same tabulation will be performed for grade 3 AEs and for AEs with relationship to mAb TB31F administration. The reports of unsolicited AEs will be reviewed by a physician and will be categorized by ICD-10. The percentage of subjects with at least one report of unsolicited AE and reported up to 28 days after mAb TB31F administration will be tabulated with exact 95% CI. The same tabulation will be performed for grade 3 unsolicited AEs and for unsolicited AEs with a relationship to mAb TB31F administration. SAEs will be described in detail. Withdrawals due to AEs/SAEs will also be summarized. Vital signs which are outside of the normal range and clinically significant will also be listed in tables. The frequency of signs and symptoms will be compared between groups with the chi-square test or fishers exact test. Serious adverse events (SAEs) occurring at any point during the trial will be summarized and relatedness to vaccine will be assessed.

Clinical Laboratory Data Analyses

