13.2 Update of risk assessment for amendment v1.6 (prior to group 5)

Following TB31F administration in groups 1-4, the following update of the risk assessment can be made:

a. Level of knowledge about mechanism of action

TB31F has been administered intravenously to n=20 subjects in groups 1-4. No ADA have yet been measured.

b. Previous exposure of human beings with the test product(s) and/or products with a similar biological mechanism

TB31F has been administered intravenously to n=20 subjects in groups 1-4. Administration is safe and well-tolerated at all administered doses including in the 5 volunteers at the highest dose of 10mg/kg. There have been no grade 3 AEs or SAEs for any of the dosage groups. Two out of 20 volunteers reported local solicited adverse events, both grade 1. The most common general solicited adverse event was grade 1 or 2 fatigue on day of TB31F administration in 12 out of 20 volunteers. Fatigue is a known side-effect of the pre-medication clemastine. TB31F has not previously been administered intradermally, subcutaneously or intramuscularly.

c. Can the primary or secondary mechanism be induced in animals and/or in ex-vivo human cell material?

No change.

d. Selectivity of the mechanism to target tissue in animals and/or human beings

No change.

e. Analysis of potential effect

Preliminary analysis shows that there is a TRA of approximately 50% in group 1 (0.1 mg/kg) at end of infusion. In group 2 (1 mg/kg), TRA of >95% is maintained up to day 28 after TB31F administration.

f. Pharmacokinetic considerations

The pharmacokinetic evaluation in human subjects will be analyzed from human sera collected at several time points after TB31F administration. See time and event table for details. Preliminary analysis of TB31F concentrations in serum over time indicate a half-life of approximately 20.5 days, in line with other human IgG1 molecules.

g. Study population

No change.

h. Interaction with other products

No change.

i. Predictability of effect

Preliminary analysis of the SMFA in group 1 (0.1mg/kg) show a TRA of approximately 50% at end of infusion. With the dosage of group 2 (1mg/kg), a TRA of more than 95% was maintained up to day 28 after administration.

The subcutaneous dosage of 100 mg mAb TB31F is predicted to have >80% inhibition of the development of oocyst stage parasites in the mosquito with >80% 28 days after administration.

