**Analyses in relation to endpoints**

**Safety outcome analyses:**

- For each solicited (local or general) adverse event type, the number and proportion of subjects experiencing that AE within the Protocol-defined timeframe will be tabulated by severity grade for each dose group and for the entire study population. This will also be tabulated for subjects experiencing any solicited local, any solicited general and any solicited AE (see example table below). Where applicable, we will compare these proportions between groups. Relatedness (possibly, probably or definitely) of solicited AEs to TB31F administration may also be presented. (Outcome measures 1 and 2).
- For each unsolicited adverse event type (categorized by ICD-10), the number of events per dose group and overall study population will be described categorized by severity grade and relation to TB31F administration. (Outcome measure 4).
- The proportion of individuals with grade 1, 2 and 3 adverse events may be compared between groups (Outcome measures 1,2,4) .
- The total number of grade 1, 2 and 3 adverse events as count data may be compared between groups.
- Individual serious adverse events (SAEs) will be summarized, including relatedness to TB31F administration (Outcome 5).
- Withdrawals due to AEs/SAEs will be summarized per group.

Table - Descriptive statistics for subjects experiencing solicited AEs

|               |           | Group 1   |   | Group 2   |   | Group 3   |   | Group 4   |   | Group 5   |   | All       |   |
|---------------|-----------|-----------|---|-----------|---|-----------|---|-----------|---|-----------|---|-----------|---|
|               |           | #Subjects | % | #Subjects | % | #Subjects | % | #Subjects | % | #Subjects | % | #Subjects | % |
| Local AE1     | Grade 1   |           |   |           |   |           |   |           |   |           |   |           |   |
|               | Grade 2   |           |   |           |   |           |   |           |   |           |   |           |   |
|               | Grade 3   |           |   |           |   |           |   |           |   |           |   |           |   |
|               | Any grade |           |   |           |   |           |   |           |   |           |   |           |   |
| Local AE2     | Grade 1   |           |   |           |   |           |   |           |   |           |   |           |   |

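### The pooled local adverse-event rate, and any between-group test not restricted by route, mix intravenous with subcutaneous administration, so a route effect could be read as a dose effect

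*Protocol*

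**What the plan says.** Number and severity of solicited local events through day 7 is the first primary endpoint (Protocol 2.3; SAP, Safety outcome measures). Protocol 9.4.1 gives one definition for every group: "Pain at injection site and redness/swelling at injection site".

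The sites behind that definition differ by route.

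- Groups 1-4 receive TB31F by infusion through a venous catheter.
- Group 5 receives it as two subcutaneous injections of about 1 mL. If the product is diluted, the total is 4 mL at about 1 mL per site, so about four sites (Protocol Table 6a footnote).
- The catheter instruction in Protocol 8.3.4 exempts no group: "The subject will have one or two intravenous dwelling catheters inserted into the antecubital vein of the arm".
- For self-examination after discharge, Protocol 8.3.4 says "subjects will be asked to examine the site of infusion and record local signs and symptoms for seven days". Protocol 8.3.5 refers to the injection site instead. Neither sentence distinguishes the routes.

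On analysis, Protocol 10.1 asks for results by group and overall, with exact 95% intervals for the percentage of subjects with local events, and adds: "The frequency of signs and symptoms will be compared between groups with the chi-square test or fishers exact test". The SAP says that solicited events "will be tabulated by severity grade for each dose group and for the entire study population". Its table shell has one column for each of groups 1 to 5 and a column headed All, and these run through the individual local rows and the 'Any local AE' rows. The SAP makes the comparison of proportions conditional on its being applicable, without saying which groups would be compared.

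Protocol 13.2 already reports the intravenous result: "Two out of 20 volunteers reported local solicited adverse events, both grade 1".

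**The concern.** A local reaction at a vein that has received an infusion and a local reaction at an abdominal injection site are different tolerability outcomes. In groups 1-4 the counted site is also a catheter site, and Protocol Table 5 lists pain from catheter placement as a risk of the procedure, separate from the product. In group 5 the product goes into tissue at two or more sites.

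Groups 1-4 differ from one another by dose. Group 5 differs from all of them by route, by number of sites and by fixed dosing. A rate pooled over all five groups is therefore a weighted average of two routes, with weights set only by the 20:5 allocation. A test of equal frequency across five groups can reject because of route alone. In a trial presented as dose escalation, a reader could take that for a dose signal. Protocol 6.4.1 names local reactogenicity as the new risk of subcutaneous administration, so this is where the two routes are most likely to differ.

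**Working it through.** **Inputs.** Five subjects per group ("Each group will include five subjects", Protocol 4.4), so 20 intravenous and 5 subcutaneous. Intravenous local events 2/20 (Protocol 13.2), assumed final. Subcutaneous events k = 0 to 5, unknown. Significance level 0.05 (SAP, Confidence intervals and P values).

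**The plan's own figures.** The sample-size statement rests on n=20. 1 − (1 − 0.1087)^20 = 0.900 and (1 − 0.0052)^20 = 0.901, so both stated rates reproduce. They do not test the present point, but they show that the planned denominator was the 20 intravenous subjects.

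**Pooled rate.** All = (2 + k)/25 = 0.8 × 10% + 0.2 × (subcutaneous rate). A move of 20 percentage points in the subcutaneous rate shifts 'All' by only 4 points. The intravenous rate is 2/20 = 10.0% (Clopper-Pearson 95% CI 1.2% to 31.7%).

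| k | SC rate (95% CI) | All (95% CI) | Fisher p, IV 2/20 vs SC k/5 | Five-group exact p, the two IV events in different groups | Five-group exact p, both IV events in one group |
|---|---|---|---|---|---|
| 0 | 0% (0 to 52.2) | 8% (1.0 to 26.0) | 1.0 | 1.0 | 0.167 |
| 1 | 20% (0.5 to 71.6) | 12% (2.5 to 31.2) | 0.504 | 1.0 | 0.457 |
| 2 | 40% (5.3 to 85.3) | 16% (4.5 to 36.1) | 0.166 | 0.753 | 0.160 |
| 3 | 60% (14.7 to 94.7) | 20% (6.8 to 40.7) | 0.038 | 0.188 | 0.047 |
| 4 | 80% (28.4 to 99.5) | 24% (9.4 to 45.1) | 0.0055 | 0.033 | 0.006 |
| 5 | 100% (47.8 to 100) | 28% (12.1 to 49.4) | 0.0004 | 0.002 | 0.0004 |

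'All' runs only from 8% to 28% while the subcutaneous rate runs from 0% to 100%. From k = 2 upward, the pooled interval does not contain the observed subcutaneous rate.

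**Route read as dose.** Take k = 4 with the two intravenous events in different groups: the five-group exact test gives p = 0.033. Now restrict the same data to groups 1-4. Two events among 20 subjects can fall in C(20,2) = 190 ways: 6 × 5 × 5 = 150 with the events in different groups and 4 × C(5,2) = 40 with both in one group. Tables of the first kind have probability 25/190 each, of the second kind 10/190 each. So p = 1.0 if the events are in different groups and 40/190 = 0.21 if they are in the same group. Neither arrangement shows a dose signal among the intravenous groups; the small five-group p-value comes from adding group 5.

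**Number of sites alone.** Assume equal, independent risk p at each site and one intravenous site. Per-subject risk for m sites is 1 − (1 − p)^m.

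- At p = 10% this is 10.0%, 19.0% and 34.4% for 1, 2 and 4 sites.
- 'All' then moves from 10.0% to (20 × 10% + 5 × 19%)/25 = 11.8%, or to 14.9% with four sites.
- Over p = 5% to 30%, two sites move 'All' by about 1 to 4 points (5.0% to 6.0%; 30.0% to 34.2%).

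Site count by itself therefore distorts the pooled rate little. A route difference in the risk per site would matter more.

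**The case against.** The strongest reply is that the plan already reports by group. Group 5 has its own column, the unit is the subject, Protocol 10.1 calls the safety analyses descriptive, and both documents acknowledge that comparisons are underpowered. No dose decision depends on the test. Events also carry a causality assessment, and Protocol 10.1 tabulates related events separately. All of this stands and limits the point: a reader might infer that the primary local result as a whole is mixed, and it is not.

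Three further inferences are tempting and also fail.

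- **Group 5 is watched more closely.** The update to Protocol 6.4.1 says "Every injection will be carefully monitored to evaluate the occurrence of local adverse events". But the staff review of solicited local symptoms on the dosing day and at 24 hours (Protocol 8.3.4), the 60 minutes of direct observation (8.3.17) and the diary review at each visit (8.3.5) apply to every group. Group 5 does have an added day-4 visit, but Protocol section 3 describes it as one for pharmacokinetic and pharmacodynamic sampling. That is too little to support a claim of different monitoring.
- **Catheter reactions in group 5 are lost to the endpoint.** No section says so. The documents do not state which site counts for each route. An unsolicited local event would still appear in the tabulation in Protocol 10.1, which covers solicited and unsolicited local events together.
- **The SAP commits to a five-group test of local events.** It does not; its comparison is conditional. The unrestricted commitment is in Protocol 10.1, and neither text limits a comparison to one route.

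It is also fair to say that two injection sites are part of giving the 100 mg dose, so a per-subject rate is a proper tolerability measure for group 5. That supports reporting it separately, not averaging it with the infusion groups.

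**Conclusion.** The point holds in a limited form, as an inexpensive improvement. The pooled local-event rate with its interval describes neither route, and an unrestricted five-group test of local events confounds route with dose. The group-specific results are sound and the subcutaneous rate can be read directly.

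In size, 'All' is confined to 8% to 28% whatever happens in group 5, and with four subcutaneous events a five-group p-value of 0.033 or less would arise with no dose signal in groups 1-4. This rests on the 2/20 count being final; the values of k are illustrations, not predictions. The site-count figures also assume equal, independent risk per site and play only a small part in the conclusion.

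**What to change.** In the SAP (Safety outcome analyses, text and table shell) and in Protocol 10.1:

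1. For the individual local rows and the 'Any local AE' rows, replace 'All' with 'All IV' (groups 1-4, n=20) and 'SC' (group 5, n=5), each with its exact 95% interval. The column for all 25 subjects can stay for general events.
2. Limit dose comparisons of local events to groups 1-4. Label any contrast of group 5 with the intravenous groups as a route comparison.
3. State that the site counted is the TB31F administration site for each route, and list reactions at other catheter sites separately where source notes record them.

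The cost is a revised table shell and a few sentences, with no extra subjects, visits or data collection. The loss is a single local-event rate for all 25 subjects. Groups 1-4 have already been dosed, so the separate listing of catheter-site reactions can only be as complete as the existing diaries and notes. The change belongs in the SAP before database lock, by which time Protocol section 10 requires it to be final.
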